## 5 RANDOMISATION & ENROLMENT PROCEDURE

### 5.1 Summary of Randomisation Process

Counselling and consent for the trial will occur when the platelet count falls below  $100 \times 10^9/L$ . Randomisation will occur when the platelet count falls below  $50 \times 10^9/L$ . Neonates will be allocated to one of the two groups by the participating clinicians at each centre using an independent centralised 24 hour web-based randomisation service, as described below. The neonate will be assigned a trial number (6 digits, the first 3 digits will be the centre number and the remaining 3 digits will be the patient number from 001 to 999), and allocated to either Arm A or Arm B. The trial number will also be entered in the screening log. The randomisation service will send confirmation to the PI of the trial number and the allocated treatment policy and inform the Trial Manager. Once the neonate has been randomised, data collection on bleeding will commence. Unless there are other clinical reasons, for neonates in Arm A, a platelet count threshold of below  $25 \times 10^9/L$  will be used as a trigger for platelet transfusion. For neonates in Arm B, a platelet count threshold of below  $50 \times 10^9/L$  will be used as a trigger for platelet transfusion.

### 5.2 Details of Registration Process and Randomisation

1. The local PI (or designate) will be responsible for identifying and consenting the parents/guardians of eligible neonates once the platelet count has dropped to  $<100 \times 10^9/L$ .
2. A screening sheet with a log number will be completed on all neonates admitted to selected participating units with platelets  $<100 \times 10^9/L$  and GA  $<34$  weeks. The log will include GA, post-natal age, birth weight and main diagnosis. It will include neonates not approached, and those neonates approached but in whom consent was not obtained for the trial (with reasons) and therefore will define how representative randomised neonates are as a group relative to the group of eligible neonates who were not randomised.
3. Eligibility for randomisation will be assessed with reference to inclusion and exclusion criteria.
4. When the neonate's platelet count falls to  $<50 \times 10^9/L$ , the PI or designate (the randomiser) will ensure a cranial ultrasound has been undertaken within the last 6 hours, and will then complete the trial registration/randomisation form and access the web based randomisation service at <http://www.sealedenvelope.com> to obtain a unique trial number and assignment of treatment policy. Before logging onto the website to randomise the neonate, the following pieces of information must be available: the neonate's gestational age at birth (in weeks and days); knowledge of presence or absence of IUGR; the most recent platelet count (which must be below  $50 \times 10^9/L$ ) and the date and time of the most recent cranial USS, which must have been undertaken within 6 hours before randomisation.
5. Following randomisation, the randomisation service will e-mail confirmation of the allocated treatment policy and trial number to the PI and Trial Manager. The PI will place the emailed allocated treatment policy in the neonate's medical notes.
6. The local PI/designate is responsible for informing the neonate's consultant and the parents of the neonate's treatment allocation, and for placing a label indicating trial participation on the cot and cover of the neonate's medical notes.

7. The local PI/designate will complete the patient's screening sheet adding the patient's trial number to the existing data. The local PI/designate will also be responsible for informing the Blood Bank of the trial number and the trial treatment allocation.
8. The treatment allocation will persist for the length of stay in the centre participating in the study. Neonates who develop repeated episodes of thrombocytopenia of less than  $50 \times 10^9/L$  will remain on the same treatment arm that they were allocated to when first enrolled.
9. Twins will be randomised separately and will be allocated to their individual treatment arm as per randomisation.

## **RANDOMISATIONS**

<http://www.sealedenvelope.com>

**Randomisations can also be undertaken through the Planet-2 website:**

[www.planet-2.com](http://www.planet-2.com)

Click on the red button in the centre of the home page to randomise

## 6. TREATMENT OF NEONATES

### 6.1 Introduction

Neonates will be allocated to one of two treatment policies (treatment arms) at randomisation. The intervention is a platelet transfusion at two different platelet count thresholds. If there is uncertainty about the accuracy of a platelet count at any time (e.g. spurious due to traumatic venesection, blood sample is reported to show clots) the peripheral blood count should be repeated.

### 6.2 Arm A Standard (platelet transfusions at platelet counts $<25 \times 10^9/L$ )

Prophylactic platelet transfusions should be given only below platelet counts of  $25 \times 10^9/L$ , for neonates with no bleeding or with only minor bleeding (**for definitions see Section 6.4 below**)

Additional platelet transfusions may be considered at the discretion of the attending neonatologist, at platelet counts higher than the allocated threshold, under the following circumstances:

- Therapeutically to treat major bleeding, following objective and documented signs of clinically relevant bleeding graded as moderate, major or severe, but **not** for minor bleeding (**for definitions see Section 6.4 below**).
- Prior to planned invasive procedures (including Suprapubic Aspiration and Lumbar Puncture but not percutaneous central lines or arterial line insertion) or major surgery where haemostasis may be critical to outcome.

Specific situations which will **not** generally be considered indications for platelet transfusion outside of the allocated threshold are as follows:

- Prior to planned insertion of percutaneous central lines or arterial lines
- Planned or current indomethacin (or ibuprofen) treatment of patent ductus arteriosus.
- Extreme prematurity without additional risk factors, irrespective of the postnatal age of the infant
- Any platelet count  $\geq 25 \times 10^9/L$ , irrespective of previous values or rate of drop, in the absence of the exceptions noted above. 'Pre-emptive' transfusing to keep the platelet count above the allocated threshold will constitute a protocol violation. In situations where the count appears to be falling, clinicians are at liberty to repeat the platelet count earlier than planned if concerned about an impending drop below the threshold.

All instances of platelet transfusion outside this study protocol must be recorded on the daily transfusion data collection form.

### 6.3 Arm B Intervention (platelet transfusions at platelet counts $<50 \times 10^9/L$ )

Prophylactic platelet transfusions should be given only below platelet counts of  $50 \times 10^9/L$ , for neonates with no bleeding or with only minor bleeding (**for definitions see Section 6.4 below**)

Additional platelet transfusions may be considered at the discretion of the attending neonatologist, under the following circumstances:

- Therapeutically, following objective and documented signs of clinically relevant bleeding graded as moderate, major or severe, but **not** for mild bleeding (**for definitions see Section 6.4 below**).
- Prior to planned invasive procedures (including Suprapubic Aspiration and Lumbar Puncture, but not percutaneous central lines or arterial lines) or major surgery where haemostasis may be critical to outcome.

Specific situations which will **not** generally be considered indications for platelet transfusion outside of the allocated threshold are as follows:

- Prior to planned insertion of percutaneous central lines or arterial lines
- Planned or current indomethacin (or ibuprofen) treatment of patent ductus arteriosus.
- Extreme prematurity without additional risk factors, irrespective of the postnatal age of the infant
- Any platelet count  $\geq 50 \times 10^9/L$  irrespective of previous values or rate of drop, in the absence of the exceptions noted above. 'Pre-emptive' transfusing to keep the platelet count above the allocated threshold will constitute a protocol violation. In situations where the platelet count appears to be falling, clinicians are at liberty to repeat the platelet count earlier than planned if concerned about an impending drop below the threshold.

All instances of platelet transfusion outside this study protocol must be recorded on the daily transfusion data collection form.

[figure not shown]
## 6.4 Definitions of Bleeding Grades including IVH

IVH will be graded as shown in the table below:

Haemorrhage	
H0	No haemorrhage
H1	Germinal Layer Haemorrhage (GLH) which includes subependymal haemorrhage and localized choroid plexus haemorrhage
H2	IVH extent < 50% of the ventricle
H3	IVH extent $\geq$ 50% of the ventricle, or large intraparenchymal / intracerebral haemorrhage (i.e. > 2cms)
Ventricular size	
V0	No ventricular dilatation/ ventricular dilatation $\leq$ 12 mm
V1	Dilatation > 12 mm.
Parenchymal injury	
P0	No injury
P1	Echodensity measuring < 1 cm (max diameter in any plane)
P2	Echodensity measuring 1 – 2 cm (max diameter in any plane)
P3	Echodensity measuring > 2 cm (max diameter in any plane)
PC	Porencephalic cyst
PVL	Periventricular Leukomalacia (PVL)

Measurement of ventricular Index:

In order to assess ventricular dilatation, the ventricular index will be measured. The measurement will be taken from each side of the lateral wall of the body of the lateral ventricle to the falx, at the level of foramina of Munro. Measurement has to be in the horizontal plane as illustrated below:

For the purposes of this study, bleeding will be graded according to the following definitions:

#### **I Minor:**

Any bleed from skin, umbilical cord, skin around stoma, surgical scar, mucosa. Any pink frothy or old bleed from the ET tube. H1 haemorrhage on cranial US (Germinal Layer Haemorrhage, GLH, which includes subependymal haemorrhage and localised choroid plexus haemorrhage)

#### **II Moderate:**

Any frank bleed from the stoma, macroscopic haematuria, or, acute fresh bleed through the endotracheal tube (ETT) without ventilatory changes.

Moderate IVH is defined as

- H2 or H3 without dilatation (V0)
- H0, H1, H2, H3 with P2.

#### **III Major:**

Frank rectal defined as macroscopic faecal bleed (not if only occult positive). Pulmonary bleed defined as acute fresh bleed through the endotracheal tube (ETT) associated with increased ventilatory requirements or the need for intubation and ventilation.

An intracranial bleed is defined as a major bleed if any of the following apply:

Neurosurgical intervention is required

Radiological imaging showing a midline shift

Clinical signs and symptoms of a deficit with significant derangement of laboratory investigations.

Major IVH is defined as

- H2 or H3 with ventricular dilatation (V1)
- H1, H2, H3 with parenchymal involvement (P3)
- Any evolution of intracranial haemorrhage to H2V1, H3V1, or (H1, H2, H3) with parenchymal involvement (P3)

#### **IV Severe:**

Fatal major bleeding or shock is defined as life threatening major bleed associated with hypotension, hypovolaemia or any other haemodynamic instability and/or bleeding requiring volume boluses or red cell transfusion in the same 24 hours.

## **6.5 Platelet prescribing and dose**

The platelet transfusion dose will be 15ml/kg. Platelets for neonates will be issued from the hospital blood bank according to local standard operating procedures.

Current UK specifications for apheresis platelets are a platelet cell content  $>240 \times 10^9$  per unit.

## **6.6 Other blood components - Dispensing and Accountability**

Red cells, fresh frozen plasma, cryoprecipitate and other blood products (e.g. fibrinogen concentrate) will be transfused according to local departmental guidelines. Departmental policies on transfusion will be reviewed from each participating centre. Current local guidelines for vitamin K prophylaxis will be followed.

All neonatal units will have local policies in place describing the administration of blood components including platelets, which will include the management of transfusion side effects. All blood transfusion components in the UK, including red cells and platelets, are standardised and conform to national specifications. From 1999, all allogeneic blood components produced in the UK have been subjected to a pre-storage leukocyte filtration process. Normal blood bank procedures will be followed for stock control and issuing of platelet units and patient details.

## **6.7 Early stopping of the allocated treatment**

If in the clinical judgement of the attending neonatologist, an enrolled neonate cannot follow treatment allocation (e.g. a higher platelet transfusion threshold is clinically warranted), the case should be discussed with the joint chief investigator or one of the medical experts. Irrespective of the clinical decision, data collection should continue, aiming to complete data collection at least up to study day 28. Reasons for deviation from the randomised treatment allocation will be recorded.

## **6.8 Other Medications**

Any clinically-indicated medication is permitted during the time the patient is in the PlaNiT-2 trial; there are no restrictions on concomitant medications.

## **7. ASSESSMENTS AND PROCEDURES**

### **7.1 Introduction**

It will be the responsibility of the local researcher(s) to identify eligible neonates with a platelet count below  $100 \times 10^9/L$ , using the patient eligibility checklist. Having identified an eligible neonate, the local PI or designate (e.g. research nurse) will approach the parents or guardians to discuss the trial using the patient information sheet and to seek their consent. Once informed consent has been obtained, a copy of the signed consent form and a copy of the Parent Information Leaflet (PIL) should be given to the parent. The local researcher should keep the original consent document in the site file and a copy must be filed in the neonate's medical notes.

Data collection will be the responsibility of the local clinical team led by the local PI and study co-ordinator at each site. Data will be recorded on paper record Case Report Forms (CRFs) which will be transferred onto MACRO Trial Manager Software at the CTU. CRFs will be used to collect data from study entry. Three patient identifiers (Patient ID allocated at randomisation, initials and date of birth) will be used on all CRFs.

## 7.2 Schedule of Assessments

Assessment to be performed	Pre-randomisation (a)	At randomisation (b)	Study Day																SD 29 to End of Study	2 year follow up
			1	2	3	4	5	6	7	8	9	10	11	12	13	14	21	28 (d)		
Registration	X																			
Informed Consent	X																			
Randomisation		X																		
Cranial USS (c)		X							X							X	X	X	X	
Daily bleeding Assessment			X	X	X	X	X	X	X	X	X	X	X	X	X	X				
Transfusion adverse event form			X	X	X	X	X	X	X	X	X	X	X	X	X	X	X	X	X	X
Weekly assessment form(d)																	X	X	X (f)	
Serious Adverse Events			X	X	X	X	X	X	X	X	X	X	X	X	X	X	X	X	X	X
End of Study Form (e)																			X	
TRPG/SEND/NNAP 2-year corrected age outcome form																				X

a: Registration and consent when platelet count falls below  $100 \times 10^9/L$

b: Randomisation when platelet count falls below  $50 \times 10^9/L$

c: Cranial USS: to be performed no more than 6 hrs pre randomisation and at least weekly thereafter up to STUDY DAY 28. Thereafter scans are at the discretion of the clinicians apart from an End of Study Scan which must be undertaken within 7 days prior to discharge. (refer to s7.11)

d: Weekly assessment will be completed until End of Study. Collect data on major bleeds, mortality, cranial USS, platelet count, platelet transfusion, NEC and sepsis. For babies discharged home before study D28 a telephone call will be made to parents around SD28 in order to monitor any further AEs / SAEs that have occurred since discharge providing prior consent to contact has been given (refer to s.1.1.5 & s.7.6)

e: End of study form: An End of Study form will be completed at the time of death, NICU discharge home, 38 weeks CGA or at Study Day 28 if this is later (for those neonates recruited after 34 weeks CGA). For neonates transferred whilst on the study to another unit participating in Planet, data collection will continue to End of Study (refer to s1.1.5)

f: The first weekly data collection form to be completed after SD 28 is on SD 35.

### 7.3 Procedures for data collection

Assessments will be performed according to the schedule in Section 7.2. Prime responsibility for the complete collection of data for each centre will reside with the local PI but may be delegated (e.g. research nurse). Overall responsibility for collating data from all centres will reside with the Trial Manager. Local centres will send copies of completed CRFs to the CTU Data Manager, at Study Day 28 and then at End of Study. The procedure for SAE reporting is detailed in Section 9.

### 7.4 Randomisation

Background data will be collected before or at the time of randomisation including:

- gestational age at birth
- weight at birth
- gender
- postnatal age in days
- weight at enrolment
- co-existing or prior medical conditions/ diagnosis including major bleeds, IUGR, NEC  $\geq$  Stage 2 defined as per Bell's criteria (Bell et al; 1978) and sepsis

Once final eligibility is confirmed, the neonate will be randomised into the study according to the procedures described in Section 5

### 7.5 Data for daily bleeding and outcome assessments up to 14 days

A bleeding assessment form will be completed daily for all study subjects for 14 days after randomisation. The daily bleeding assessment will be performed by the local PI or designate e.g. research nurse (RN) or research staff or other ward staff as agreed locally. The first bleeding assessment form completed within 24 hours after randomisation will be Study Day 1. The PI and designated staff completing the daily bleeding assessments will receive training and have guidance notes to help them collect these data. Particular attention will be given to the repeated training of local designated site staff in the correct use of the bleeding assessment tool.

For the purposes of this trial, the period of observation for daily data collection is defined as:

- From study day 1 (within 24 hours after randomisation; when platelet count below  $50 \times 10^9/L$ ) and ending at study day 14, or death whichever is earlier

Information on clinical bleeding outcomes and transfusions will be collected prospectively through clinical assessment and interrogation of patient case records undertaken by the local designated site staff on a daily basis for the complete period of observation. The daily CRF for the collection of clinical bleeding outcomes and transfusions is based on a modified version of the bleeding assessment tool adapted for neonates from the WHO bleeding assessment tool and the results of the multi-centred prospective PlaNeT-1 study.

Decisions regarding prophylactic platelet transfusions will be made by ward staff on the basis of the baby's platelet count as outlined in the flow chart for both arms of the trial, shown at start of section 5. There may be situations where clinicians give additional platelet transfusions not according to the trial flow chart and these will be recorded (see 6.2, 6.3 above).

## **7.6 Data for major bleeding and outcome assessments from study day 14 until discharge: weekly data collection**

For neonates still in hospital at study day 14, daily data collection will cease and a weekly data collection form will then be started and continued until the time of death, discharge home, 38 weeks CGA or at Study Day 28 if this is later (for those neonates recruited after 34 weeks CGA). This will be regardless of whether the neonate's thrombocytopenia has resolved or whether the neonate has further episodes of thrombocytopenia (see 7.7). The weekly form will collect data on new major bleeds, mortality, platelet counts, platelet transfusions, NEC, sepsis extravasation injuries and adverse events related to platelet transfusions, including those reported to the UK national haemovigilance reporting schemes (SHOT and SABRE, see 8.3.2)

## **7.7 Neonates with further episode(s) of thrombocytopenia after study day 14**

After randomisation, allocation will apply for the entire inpatient stay, including for neonates that develop new episodes of thrombocytopenia after study day 14, until 38 weeks CGA or at Study Day 28 if this is later. Neonates who have a further episode of thrombocytopenia  $<50 \times 10^9/L$  will therefore remain in the same treatment arm that they were allocated to when first enrolled. Daily bleeding assessment forms are not required after Study Day 14 even if thrombocytopenia recurs but weekly assessment forms will be completed (see Figure 7.2).

## **7.8 Neonates with platelet counts that remain $<50 \times 10^9/L$ after study day 14**

Some neonates will have platelet counts that remain  $<50 \times 10^9/L$  at the end of the 14 day daily data collection period. It is envisaged that there will be sufficient daily bleeding assessment data on these neonates for detailed analysis and comparison with other patient groups. Therefore daily data collection will stop at this point as with neonates whose platelet count has recovered. Data collection will continue weekly until End of Study (Section 7.6).

## **7.9 Neonates transferred out of the participating unit**

A log will be kept of neonates transferred out of a participating unit to another unit. For neonates transferred to a non-participating (receiving) unit before reaching Study Day 28, basic information will be requested in order to obtain the primary outcome data. A data collection form will be sent with the baby to the receiving unit with a copy of the consent form, requesting information on number of platelet transfusions, occurrence of any safety events and the results of any imaging -5 / +10 days of SD28. The local research nurse from the recruiting site will be responsible for liaising with the staff in the receiving unit. The trial manager will be available for any queries. The receiving unit will be asked to send pseudo-anonymised primary outcome data back to the recruiting centre who will in turn pass the information on to the NHSBT CTU. After this point no further information will be requested.

For babies transferred to a non-participating unit after Study Day 28, (post primary outcome), no data will be requested from the receiving unit.

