### **7.11 Cranial ultrasound scans**

Each centre must have the capability to conduct cranial USS at any time, 24 hours a day. Cranial USS required are as follows:

- a) Within 6 hours prior to randomisation
- b) Thereafter, a minimum of weekly USS (+/-3 days) should be performed until study day 28 or prior to discharge if earlier
- c) For neonates who remain in hospital longer than 28 days, any scan performed should be recorded in the weekly assessment form and a final USS should be done prior to discharge.

The data to be collected from the USS reports and recorded in the bleeding assessment tool / weekly assessment forms (to be filled in as per the guidance of the bleeding assessment record guidance notes) are as follows:

- Evidence of intracranial haemorrhage and its extent
- Ventricular Size
- Parenchymal injury and grade.

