### **In cases where no imaging is performed within -5 / + 10 days of SD28:**

- If a baby is discharged home well and not readmitted prior to SD28, we will assume no MB had occurred by SD28.
- For babies discharged home after SD28, we will assume that no new major cranial bleed had taken place by SD28 if other Cranial Ultrasound (CUSS), CT or MRI scans performed on or between SD14 and discharge showed no new major bleeding providing that there was no documented episode of any significant clinical deterioration (e.g proven sepsis, NEC, or collapse) that required transfusion with blood products, or evidence of other new major bleeding in that period.
- In cases where no subsequent pre-discharge CUSS, CT or MRI scan was undertaken, providing that there is, prior to discharge, no documented episode of any significant clinical deterioration (e.g. proven sepsis, NEC, or collapse) that required transfusion with blood products, or evidence of other new major bleeding, then we will also assume that there was no major bleed at SD28.
- All other cases are to be dealt with on a case by case basis
- Review of evidence in the first case by [name], Joint Chief Investigator. Further review to be undertaken by medical experts within TMG.
- For difficult cases it may be necessary to refer to an independent neonatologist to review.

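### The imaging requested from non-participating units (SD23 to SD38) omits every receiving-unit scan that the section 9.2.1 fallback would need, so a silent major IVH in a transferred baby can be scored as no major bleed

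*Protocol*

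**What the plan says.** Section 7.9 gives the purpose of the request to the receiving unit: "basic information will be requested in order to obtain the primary outcome data". The form sent with a baby transferred before SD28 asks for the platelet transfusion count and "occurrence of any safety events and the results of any imaging -5 / +10 days of SD28". Once the data are returned through the recruiting centre, "After this point no further information will be requested". Section 1.2 has the same content. For later transfers: "For babies transferred to a non-participating unit after Study Day 28, (post primary outcome), no data will be requested from the receiving unit".

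Section 7.11 sets the scan schedule: "a minimum of weekly USS (+/-3 days) should be performed until study day 28", or until discharge if that is earlier. Section 6.4 defines major IVH from scan findings (extent of haemorrhage, ventricular dilatation, parenchymal involvement), including evolution to those grades.

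Section 9.2.1 covers babies with no imaging in the SD28 window. For those discharged home after SD28, no new major cranial bleed is assumed if "scans performed on or between SD14 and discharge showed no new major bleeding", provided that no deterioration needing blood products and no other new major bleeding occurred. If no later scan was undertaken before discharge and nothing of that kind is documented, "then we will also assume that there was no major bleed at SD28". All other cases are reviewed individually.

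**The concern.** The transfer form exists to obtain the primary outcome, but its imaging dates do not match the rule that determines that outcome. The fallback comes into play only when SD23 to SD38 is empty, and that is the only period for which the form asks for images.

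Major IVH is decided from scans and may be clinically silent. A baby who stays in a participating unit has every weekly scan recorded. A transferred baby does not, so the primary outcome is ascertained less completely after transfer. Because the no-scan branch treats absence of documentation as negative evidence, a gap in the request can turn into a recorded non-event. At stake are a few major bleeds in the composite and some dilution of the difference between the arms.

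**Working it through.** **1. Dates side by side**

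- Requested window (1.2, 7.9): SD28 − 5 = SD23 to SD28 + 10 = SD38.
- Scans used by the fallback (9.2.1): SD14 to discharge.
- Condition for using the fallback: no imaging in SD23 to SD38.
- Receiving-unit scans the fallback can then use: SD14 to SD22 (22 − 14 + 1 = 9 days) and SD39 to discharge. Neither range is requested.
- If transfer came before SD14, receiving-unit scans up to SD13 are not requested either, although a major bleed on one of them would count towards the outcome.

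The scans the rule needs from the receiving unit and the scans the form requests have no overlap.

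**2. Events side by side**

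- Section 9.2.1 uses proven sepsis, NEC, collapse, blood products given for them, and other new major bleeding.
- The form asks for safety events and the number of platelet transfusions. Section 8.1 places bleeding, transfusion-related events, NEC and sepsis within safety reporting, so most of these are covered in substance.
- Not named on the form: major bleeds, collapse, and blood products other than platelets. Section 8.2 keeps major bleeds out of SAE reporting, and an outside unit may not know the trial's meaning of a safety event.

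**3. Transfers after SD28**

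Under section 7.11 the day-21 scan may fall on SD18 to SD24 and the day-28 scan on SD25 to SD31. A baby last scanned on SD18 to SD22 and moved on SD29 to SD31, before the day-28 scan, is within schedule but has no image in the window. Any image taken later, up to SD38, would qualify, yet nothing is requested.

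**4. The plan's own sample size**

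Inputs from section 9.3: 20% against 12%, two-sided 5%, 80% power. With pooled variance and mean proportion 0.16:

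n = [1.960 × √(2 × 0.16 × 0.84) + 0.842 × √(0.20 × 0.80 + 0.12 × 0.88)]² / 0.08² = 329 per group after rounding up.

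This matches the protocol. At 330 per arm (660 in total), power is 80.2%.

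**5. Size under assumption**

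The documents give neither a transfer rate nor a miss rate. Let f be the share of all primary-outcome events wrongly scored as no event, equal in both arms. The rates become 0.20(1 − f) and 0.12(1 − f). Planned events are 330 × (0.20 + 0.12) = 105.6, so missed events are 105.6 × f.

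| f (assumed) | Arm A | Arm B | Events missed | Power at 330 per arm | n per arm for 80% |
|---|---|---|---|---|---|
| 1% | 19.8% | 11.9% | 1.1 | 79.7% | 333 |
| 2% | 19.6% | 11.8% | 2.1 | 79.2% | 337 |
| 5% | 19.0% | 11.4% | 5.3 | 77.7% | 350 |
| 10% | 18.0% | 10.8% | 10.6 | 75.1% | 373 |

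**The case against.** The case against is that the protocol has several safeguards and the affected group is small.

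- **Events.** A reader might infer that the form leaves out the clinical events altogether. It does not: given section 8.1, asking for safety events covers bleeding, NEC and sepsis. What remains is that collapse and non-platelet blood products are not named, and that a silent IVH seen only on a scan need not be reported as an event.
- **Default.** A reader might infer that a transferred baby automatically becomes a non-event. That is too strong. Pre-transfer scans are held by the recruiting site, an image at SD23 to SD38 may show an earlier bleed, the no-scan branch refers to scans not undertaken, and other cases go to the joint chief investigator, trial experts and if necessary an independent neonatologist. Sections 1.2 and 7.12 also allow possible use of the national database. However, reviewers cannot tell a scan that was not requested from one that was not done, and the database is meant for outcomes that could not be obtained, not for those already scored.
- **Direction.** A reader might infer that the error always lowers the count. The documents do not support this: images are accepted to SD38 while the outcome closes at SD28, so a bleed arising on SD29 to SD38 could be counted in error.
- **Transfers after SD28.** These babies were under trial observation for the whole outcome period. The gap is confined to those moved before their SD28 image.
- **Size.** In the earlier observational study (PlaNeT-1), major haemorrhage occurred in 13% of severely thrombocytopenic neonates and 53% of it was intraventricular (section 2.1), so about 0.13 × 0.53 = 7% over the whole study. Most major bleeds came within 14 days of birth (section 1.2). Section 9.3 expects higher rates here, but late bleeds visible only on a scan after transfer are probably few. This favours the lower rows of assumed f.

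These points limit the consequence. None of them closes the mismatch in imaging dates.

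**Conclusion.** The point holds for imaging. Following sections 1.2 and 7.9 exactly means that the receiving-unit scans on which section 9.2.1 relies are never requested, and a clinically silent major IVH can be scored as no major bleed. A smaller version applies to babies moved just after SD28 with no image in the window.

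The likely effect is some under-counting of major bleeds and dilution of the difference. Its size cannot be derived from the documents. Under the assumption of equal loss in both arms, missing 1% to 10% of events lowers power from 80.2% to between 79.7% and 75.1%. Section 9.3 makes no allowance for loss.

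A reader might also infer bias between the arms. That would need transfer or scanning to differ by arm, which the documents neither show nor exclude. This is a modest weakness with a cheap remedy, and it does not undermine the planned comparison.

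**What to change.** - **Sections 1.2 and 7.9, transfers before SD28:** request dated reports of all cranial imaging from transfer to discharge, at least through SD38. Alongside safety events, name major bleeds, collapse and all blood products given.
- **Sections 1.2 and 7.9, transfers after SD28:** send the same form with any baby who has no image yet within the SD28 window.
- **Section 9.2.1:** for transferred babies, apply the no-scan branch only when the receiving unit confirms that no scan was done. Otherwise send the case to the existing individual review. Coding the outcome as missing whenever a form is not returned is not recommended: it would discard other usable evidence in a trial with no allowance for loss.

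The cost is a few more lines on the form and slightly more chasing of receiving units. No extra scans are needed and the planned 660 is unchanged.
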